### 5.4 Dose delays, modifications or discontinuation for hematologic side effects

**5.4.1 Thrombosis/Embolism:** Subjects who experience a deep venous thrombosis or a pulmonary embolus, a TIA or stroke, or a myocardial infarction at any time while on eltrombopag will discontinue the drug and go off study. Subjects with platelet counts of > 50,000/ $\mu$ L at the time of thrombosis will be treated with enoxaparin or another appropriate anticoagulant as clinically indicated until the platelet count drops below 20,000/ $\mu$ L with discontinuation of eltrombopag. They will be treated for the thrombotic event as otherwise clinically-indicated.

**5.4.2 Peripheral blood smear shows new morphological abnormalities:** The presence of persistent morphologic abnormalities (red cell teardrop forms or nucleated red blood cells; immature white blood cells) or the development of significant worsening of anemia or neutropenia while on study will require discontinuation of eltrombopag and performance of a bone marrow examination to assess for development of abnormal fibrosis or progression to RAEB-2 MDS or AML.

**5.4.3 Thrombocytosis or erythrocytosis.** Patients will have eltrombopag discontinued for one week if platelets increase to >400,000/ $\mu$ L or Hb to > 16 gr/dL, and if counts have fallen below these cutoffs, drug can be restarted at 50% dosage.

### 5.5 Extended access to study drug

Subjects with response at week 16 or week 20 may continue study medication (extended access) per dosing criteria given in section 5.2.

Since there are currently no guidelines for length of therapy with eltrombopag in this subject population, drug administration for each responding subject may be continued for as long as the study remains open if there is clinical benefit to the subject and no contraindication to the

continuation of therapy or new information available from the literature to suggest that a shorter duration of therapy would be effective.

While on extended access, participants may have drug tapered, stopped, and/or re-started. The criteria for dose adjustments during the extended access phase are:

Once platelets  $>50,000/\mu\text{L}$ , Hb  $> 10 \text{ g/dL}$  in the absence of transfusions, and neutrophils  $> 1,000$  for more than 8 weeks, eltrombopag will be discontinued. If platelets drop to  $<30,000/\mu\text{L}$ , Hb to  $<9\text{g/dL}$ , or ANC to  $<500/\mu\text{L}$  the dose can be re-initiated back to the full dose. Once count stabilization again occurs, a slow dose reduction by 50 mg increments can be performed to identify the lowest dose necessary to keep counts over these thresholds.

If subjects have drug stopped on extended access due to robust response, and maintain the response, they will be taken off study after two years.

After the study is closed, the principal investigator will not provide additional doses of eltrombopag. The research team will help arrange follow-up care with the referring physician.

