## 5. TREATMENT PLAN

### 5.1 Administration of study drug (eltrombopag)

Subjects will initiate study drug at 50 mg orally once a day, taken on an empty stomach one hour before or at least two hours after a meal as detailed in section 5.8. Subjects of East Asian ancestry such as Japanese, Chinese, Taiwanese and Korean subjects will initiate study drug at 25 mg orally once a day.

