**Dose Adjustments for Patients Entering with Platelets  $\leq$  30,000/ $\mu$ L or transfusion-dependence:**

Depending on response and/or tolerability, the daily dose may be increased or decreased according to the following rules:

Platelet Count <math>\leq</math> 30,000/<math>\mu</math>L or transfusion-dependent at baseline	Dose Adjustment or Response
<20,000/ $\mu$ L above base line or platelet transfusion requirement has not decreased following at least 2 weeks of eltrombopag	Increase daily dose by 25 mg (25 mg for East Asians) every 2 weeks to 150 mg/day for non East Asians (75mg/day for East Asians).
$\geq$ 20,000/ $\mu$ L above baseline but $\leq$ 200,000/ $\mu$ L following at least 2 weeks of eltrombopag	Keep at current dosage.
>200,000/ $\mu$ L (untransfused) at any time on study	Decrease dosage by 25 mg (25 mg for East Asians) every 2 weeks to lowest dosage that maintains platelet count $\geq$ 20,000/ $\mu$ L above baseline.
>400,000/ $\mu$ L (untransfused) at any time on study	Discontinue eltrombopag for one week, if platelets < 20,000; restart at 50% of current dose.

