**Dose Adjustments for Patients Entering with Anemia (Hb < 9.0gr/dL or transfusion-dependence)**

Depending on response and/or tolerability, the daily dose may be increased or decreased according to the following rules.

Hemoglobin < 9.0 gr/dL or transfusion dependent at baseline	Dose Adjustment or Response
hemoglobin rise of < 1.5 g/dL.	Increase daily dose by 25 mg (25 mg for East Asians) every 2 weeks to maximum 150mg/day for non- East Asians (75mg/day for East Asians).
$\geq$ 1.5g/dL above baseline but $\leq$ 13g/dL following at least 2 weeks of-eltrombopag	Keep at current dosage.
>13g/dL (untransfused) at any time on study	Decrease dosage by 50% to lowest dosage that maintains Hb $\geq$ 1.5g/dL above baseline.
>15g/uL (untransfused) at any time on study	Discontinue eltrombopag for one week, if Hb<13g/dL restart at 50% of current dose. Phlebotomy may be performed if clinically indicated as determined by the investigator.

If after dose escalation to 150 mg (or a maximum tolerated dose below 150 mg) there is no response within the study period, treatment will be discontinued and subjects will go off study per section 8.6. In the event that a subject is transfused platelets for a count >10,000/ $\mu$ L without a medical indication during the study period, the subject may continue on study drug and the response assessment may be extended for an additional 4 weeks at the discretion of the principal investigator.

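### The optional re-taper in section 5.5 moves only in 50 mg steps, so a subject at 50 mg goes straight to zero and 25 mg is never tried

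*Combined protocol and SAP*

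**What the plan says.** Section 5.5 describes a sequence for responders in extended access.

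- **Stop.** When platelets, hemoglobin and neutrophils have all been above set levels "for more than 8 weeks, eltrombopag will be discontinued".
- **Restart.** If any of the three falls below a lower limit, "the dose can be re-initiated back to the full dose". No mg value is attached to that dose.
- **Re-taper.** After counts stabilise again, "a slow dose reduction by 50 mg increments can be performed to identify the lowest dose necessary to keep counts over these thresholds". No smaller step is given for low doses, and no interval between steps is stated.

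Low doses can occur at this stage. Section 5.1 states: "Subjects will initiate study drug at 50 mg orally once a day". East Asian subjects start lower: "Chinese, Taiwanese and Korean subjects will initiate study drug at 25 mg orally once a day". Under the section 5.2 platelet table, a subject who has responded and is not above 200,000/µL gets the instruction "Keep at current dosage", so an early responder may stay at the starting dose. Escalation is in 25 mg steps, to 150 mg (75 mg for East Asian subjects).

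The Precis and section 3 both say that dosing should be the lowest that keeps counts stable. Section 2.9 gives the aim of the taper as the lowest dose or duration that sustains counts.

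**The concern.** The re-taper exists to find a minimum effective dose, but its step equals the usual starting dose. At 50 mg the search ends without testing any lower non-zero dose. The subject has also already shown that zero does not hold the counts, because the re-taper is open only to someone who was stopped, relapsed and was restarted.

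Suppose a subject would hold counts on 25 mg. Following the step as written, that subject loses counts at zero and then returns to 50 mg, twice the dose needed (50/25 = 2). Alternatively, the investigator declines to taper and the subject stays on 50 mg. Either way there is an avoidable relapse or avoidable exposure. Extended access can last as long as the study is open, section 2.7 acknowledges a theoretical risk of progression, and section 10.3.1 carries the label's hepatotoxicity warning.

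**Working it through.** There is no stated figure to reproduce. The check is a listing of dose ladders.

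**Inputs.** Step of 50 mg (5.5). Starting doses of 50 mg and 25 mg (5.1). 25 mg escalation to maxima of 150 mg and 75 mg (5.2). The doses considered are therefore 25, 50, 75, 100, 125 and 150 mg.

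**Formula.** Next dose = current dose − step, repeated while the result is positive. The rule as written uses a step of 50 mg throughout. The proposed rule uses 50 mg above 75 mg and 25 mg at 75 mg or less, and stops from 25 mg or below.

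| Re-taper starts at | Non-zero levels below, as written | Non-zero levels below, proposed | Extra levels |
|---|---|---|---|
| 150 mg | 100, 50 | 100, 50, 25 | 1 |
| 125 mg | 75, 25 | 75, 50, 25 | 1 |
| 100 mg | 50 | 50, 25 | 1 |
| 75 mg | 25 | 50, 25 | 1 |
| 50 mg | none | 25 | 1 |
| 25 mg | none | none | 0 |

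From 150, 100 and 50 mg, the last step as written is 50 − 50 = 0. These are the cases in which 25 mg is never tried.

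**Does another section supply the missing step?** The downward rules elsewhere have different triggers:

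- Section 5.2, platelet table: "Decrease dosage by 25 mg (25 mg for East Asians) every 2 weeks to lowest dosage that maintains platelet count" is reached only above 200,000/µL.
- Section 5.2, anemia table: a 50% cut, only above hemoglobin 13 g/dL.
- Sections 5.2 and 5.4.3: a one-week stop and restart at a lower dose, only at the upper stopping counts.
- Section 5.3.2: a 25 mg reduction, only after a confirmed ALT elevation.

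None applies to a subject whose counts have merely stabilised after a restart.

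**Can the gap be recovered upward?** For the 75 to 25 mg step, yes. Section 5.5 carries the section 5.2 dosing criteria into extended access, and an inadequate response there allows 25 + 25 = 50 mg. For the 50 to 0 step, no. The stated route back from zero is the section 5.5 restart at the full dose, not at 25 mg.

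**Doses off the 25 mg levels.** The 50% rules can give 75 → 37.5 mg or 125 → 62.5 mg, and a later 25 mg increase from 62.5 gives 87.5 mg. The proposed wording covers these: 87.5 → 37.5 → 12.5 → stop, and 62.5 → 37.5 → 12.5 → stop.

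**Time cost.** From 150 to 50 mg takes two steps under both rules; 25 mg steps throughout would take (150 − 50)/25 = 4. Section 6.3 sets blood counts every 1 to 3 months. Assuming one step per interval, one extra level adds about 1 to 3 months.

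**Reach.** At the design's 30% response rate, 25 subjects give 25 × 0.30 = 7.5 responders. The documents do not say what share would reach the stop criteria, relapse, restart, stabilise and be at 50 mg.

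**The case against.** The strongest reply is that the protocol already leaves room. The taper is permitted, not required. The Precis and section 3 direct the investigator to the lowest dose that works, which is ground enough to use 25 mg. Section 2.9 speaks of lowest dose or duration, so a second trial off drug is within the aim. No evidence is given that 25 mg is active in MDS: section 2.6 says the effective dose is unknown and suggests that growth factors may need higher doses there. All of this stands and limits the weight of the point. It does not make the stated step serve its purpose at 50 mg, because an investigator would have to depart from the step to meet the aim.

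The meaning of full dose also matters. If it is the protocol maximum, no re-taper starts at 50 mg, and a non-East Asian subject meets the 50 to 0 step only third, after 100 and 50 mg. The step still occurs.

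A reader might infer three stronger points that the documents do not support:

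- **That 25 mg is a separate defect because the step exceeds the dose.** The only sensible next step from 25 mg is to stop, and the proposed rule does the same.
- **That East Asian subjects are left without a 50 mg option.** The 75 to 25 mg step is coarse, but the 25 mg increases in section 5.2 allow recovery.
- **That 25 mg is the lowest dose throughout the protocol.** Section 5.3.2 treats it so for hepatotoxicity only. The 50% rules in sections 5.2 and 5.4.3 take 25 mg to 12.5 mg, and section 11.1 lists 12.5 mg tablets.

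**Conclusion.** The point holds in a narrow form. The section 5.5 re-taper has no non-zero level below 50 mg for a subject who is at 50 mg, and zero has already failed in that subject. The size is one missing dose level. This follows from the text and needs no assumption about the drug's effect; the table's count of one extra level from every start of 50 mg or more assumes doses in multiples of 25 mg.

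How many subjects would benefit is unknown, and the number is likely to be very small. A reader might infer that the rule forces harm or bears on the trial's result. It does neither: the taper is discretionary and comes after the week 16/20 assessment, and the two-stage sample size and the safety stopping rule do not depend on it. It is a cheap improvement worth considering. The 50 mg steps at higher doses are not in question.

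**What to change.** In section 5.5, replace the single step with: by 50 mg at doses above 75 mg and by 25 mg at doses of 75 mg or less (the next step from 25 mg or below is to stop). Because the East Asian maximum is 75 mg, the smaller step then applies to all of those subjects. Do not describe 25 mg as the protocol's lowest dose.

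It would also help to say what full dose means, for example the dose in use when drug was stopped. The protocol does not settle this, and it is a clarification only.

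The cost is one sentence and no new tablet strength. The downside is one extra taper level, about 1 to 3 months more at a low dose under the interval assumption above, to be weighed against the theoretical progression risk in section 2.7. Time at higher doses does not grow.

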## 5.6 Permitted Supportive care

- Transfusion supportive care (e.g., blood and platelets) as clinically indicated.
- Hematopoietic growth factors (e.g., G-CSF or erythropoietin) as clinically indicated. Filgrastim (G-CSF) must be held for 3 weeks prior to enrollment bone marrow biopsy and prior to each study assessment bone marrow biopsy.
- Estrogens or combination oral contraceptive pills (OCPs) as indicated for uterine bleeding.
- Prophylactic antibiotics and antivirals as clinically indicated.
- Romiplostim (N-Plate) or IL-11 (Neumega) should not be administered.

## 5.7 Concurrent Medications:

**Rosuvastatin (Crestor®):** In vitro studies demonstrated that eltrombopag is not a substrate for the organic anion transporter polypeptide, OATP1B1, but is an inhibitor of this transporter in vitro and as evidenced by increased plasma rosuvastatin levels when eltrombopag and rosuvastatin were co-administered in a clinical drug interaction study. When co-administered with eltrombopag, a reduced dose of rosuvastatin should be considered and careful monitoring should be undertaken. In clinical trials with eltrombopag, a dose reduction of rosuvastatin by 50% was recommended for co-administration of rosuvastatin and eltrombopag. Concomitant administration of eltrombopag and other OATP1B1 substrates (including pravastatin, simvastatin, and lovastatin) should be undertaken with caution.

**Inhibitors of Cytochrome p450:** In vitro studies demonstrate that CYP1A2 and CYP2C8 are involved in the oxidative metabolism of eltrombopag. Trimethoprim, gemfibrozil, ciprofloxacin, fluvoxamine and other moderate or strong inhibitors of CYPs may therefore theoretically result enhanced activity of eltrombopag, however these interactions have not yet been established in clinical studies. Subjects on cyclosporine requiring prophylaxis against PCP should be given inhaled pentamidine instead of TMP/SULF. NIH SAA patients are routinely placed on pentamidine instead of TMP/SULF for PCP prophylaxis to avoid potential marrow-suppressive effects of TMP/SULF anyway. Other CYP inhibitors can be used concomitantly but with careful attention to possible increased eltrombopag activity and toxicity.

**Other medications:** Subjects may continue on any of the medications that they were prescribed prior to study enrollment for co-morbid conditions, and standard anti-infectious prophylaxis medications including valacyclovir, and voriconazole.

## 5.8 Instructions to subjects

**Timing in relation to food:** Administration of a single 50 mg-dose of eltrombopag with a standard high-calorie, high-fat breakfast that included dairy products reduced plasma eltrombopag  $AUC_{[0-\infty]}$  by 59% (90% CI: 54%, 64%) and  $C_{max}$  by 65% (90% CI: 59%, 70%). Food low in calcium [ $<50$  mg calcium] including fruit, lean ham, beef, and unfortified (no added calcium, magnesium, iron) fruit juice, unfortified soy milk, and unfortified grain did not significantly impact plasma eltrombopag exposure, regardless of calorie and fat content. Subjects will be advised to take eltrombopag on an empty stomach (1 hour before or at least 2 hours after a meal).

**Timing in relation to antacids:** Eltrombopag chelates with polyvalent cations such as aluminum, calcium, iron, magnesium, selenium, and zinc. Antacids, dairy products and other products containing polyvalent cations such as mineral supplements should not be administered less than 4 hours before, or after eltrombopag dosing to avoid significant reduction in eltrombopag absorption.

**Vigorous activities:** should be avoided, as mild trauma could result in bleeding.

## 6. CLINICAL MONITORING

### 6.1 Pre-study Evaluation

Patients will be screened for participation by signing consent to participate in a NHLBI screening protocol. Their eligibility to participate in this protocol will be determined based on the Inclusion and Exclusion criteria (Section 4) and data collected on the screening protocol. The time between determination of eligibility for this protocol and signing informed consent for this protocol should be 4 weeks or less.

Baseline status will be evaluated as follows:

- Medical History and physical examination
- Concurrent medication review
- Baseline assessments (done at screening or diagnostic workup, not repeated on study)
  - Folate level
  - B12 level
  - Iron panel (ferritin, transferrin, % saturation)
- Baseline laboratory studies (evaluations designated with an \* must be repeated within 72 hours of the first dose of study drug, all others within 6 months of study entry)
  - Complete blood count with differential\*
  - Reticulocyte count\*
  - Acute care, mineral and hepatic panels, CK, LDH, total protein and uric acid\*
  - Pregnancy test (urine or blood HCG in women of child bearing potential)\*
  - Thyroid function tests
  - Peripheral blood smear
  - Viral serologies for HIV, hepatitis B, C, HSV, EBV and CMV
  - HLA typing (if not already available)
  - DAT (direct antiglobulin test)
  - Type and screen (as clinically indicated)

Flow cytometry of the peripheral blood for GPI-cells  
Lymphocyte phenotyping (TBNK flow cytometry)

- Bone marrow aspirate and biopsy with reticulin and collagen fiber staining and cytogenetic analysis (morphology, cellularity, percentage of blast cells on aspirate), flow cytometry (at clinician discretion,) within four months of first dose of study drug

## 6.2 Monitoring study drug initiation through Week 16 or 20

Subjects will be monitored weekly as long as they remain on study drug through week 16. At a minimum, subjects must be evaluated at the NIH Clinical Center at week 16 (+/- 4 days). If subjects are kept on drug an additional 4 weeks to assess response, they must be evaluated at the NIH clinical center at week 20 (+/- 4 days). \*The week 20 evaluations will only need to be completed for subjects that are kept on drug an additional 4 weeks after week 16 to assess response.

Subjects must have weekly blood tests at the NIH or drawn by their referring health care provider. If subjects are to be followed at home for interim visits, progress notes and laboratory results from their health care provider and laboratory must be faxed to the study research nurse, at [name]. The following assessments will be done:

- Clinical assessment (weeks 4, 8, 12, 16, and 20\* +/- 4 days, if seen at the NIH CC only)
- Concurrent medication review (with each clinical assessment)
- CBC with differential (weekly +/- 4 days)
- Acute care, mineral and hepatic panels, CK, LDH, total protein and uric acid (weekly +/- 4 days) (Home MDs: electrolytes, transaminases, urea nitrogen (BUN), serum creatinine clearance, total bilirubin)
- Reticulocyte count (weekly +/- 4 days) (If seen at home, only if available)
- DAT (direct antiglobulin test) (as clinically indicated)
- Type and screen (as clinically indicated)
- Pregnancy test (urine or blood HCG) in woman of childbearing potential (4, 8, 12, 16, and 20\* weeks +/- 4 days)
- Bone marrow aspirate and biopsy with reticulin and collagen fiber staining and cytogenetic analysis at primary end point (morphology, cellularity, percentage of blast cells, and/or chromosomal analysis by PCR) (week 16 +/- 4 days or if clinical indicated)
- Flow cytometry of bone marrow aspirate (week 16 and 20\* +/- 4 days) (at clinician discretion)
- Flow cytometry of the peripheral blood for GPI-cells
- Lymphocyte phenotyping (TBNK flow cytometry 16 and 20\* weeks +/- 4 days)

## 6.3 Monitoring during extended access

Responding subjects who opt to remain on study drug (extended access) will be monitored every 1-3 months so long as they remain on study drug. At a minimum, subjects must be evaluated at the NIH Clinical Center every 12 months (+/-30 days) for up to 5 years. After 5 years, subjects will return to the NIH every other year with phone contact recorded in the medical record during the alternating year in lieu of a visit to the NIH. Subjects may be seen for interim visits at the NIH or at their referring home health care provider. Per the principal investigator's discretion, subjects will be seen by the healthcare provider for a clinical assessment every 1 – 3 months while on extended access, but will continue to have laboratory monitoring performed per the below outline. Subjects that are taken off drug due to response, but remain on study, will have the below procedures performed. Subjects who have had drug discontinued because of robust counts

as per section 5.5 will be followed for a period of 2 years unless drug is restarted as permitted in section 5.5. At the clinical investigator's discretion, participants may be evaluated more frequently if medically indicated based on disease status. If subjects are to be followed at home, progress notes and laboratory results from the home health care provider and laboratory must be faxed to the study research nurse, at [name].

- Interim clinical assessment, if seen at NIH
- Concurrent medication review (with each NIH clinical assessment)
- CBC with differential (every 1 – 3 months +/- 30 days)
- Acute care, mineral and hepatic panels, CK, LDH, total protein and uric acid (every 1 – 3 months +/- 30 days) (Home MDs: electrolytes, transaminases, urea nitrogen (BUN), serum creatinine, total bilirubin)
- Reticulocyte count (every 1 – 3 months +/- 30 days) (If seen at home, only if available)
- Pregnancy test (urine or blood HCG) in woman of childbearing potential (every 1 – 3 months +/- 30 days)
- DAT (direct antiglobulin test) (as clinically indicated)
- Type and screen (as clinically indicated)
- Bone marrow examination with reticulin and collagen staining and aspiration with cytogenetics and flow cytometry (flow cytometry at clinician discretion) (with each NIH clinical assessment)
- Flow cytometry of peripheral blood for GPI (with each NIH clinical assessment)
- Lymphocyte phenotyping (TBNK flow cytometry, with each NIH clinical assessment)

